Document Cover Page

Official Title of the Study:

Responsible Fatherhood Opportunities for Reentry & Mobility (ReFORM)

NCT Number: NCT02860988

Date of Document: September 29, 2020

Responsible Fatherhood Opportunities for Reentry & Mobility (ReFORM) Protocol

Background

Mountain Comprehensive Care Center (MCCC) in Prestonsburg, KY was recently awarded a grant from the Administration for Children and Families (ACF) as part of the Responsible Fatherhood Opportunities for Reentry and Mobility (ReFORM) Program to strengthen positive father-child engagement, improve employment and economic mobility opportunities, improve healthy relationships and marriage, and decrease barriers to successful community reentry. MCCC has a physical presence in Floyd, Johnson, Lawrence, Magoffin, Martin and Pike in eastern Kentucky and established relationships with the two targeted detention centers for pre-release services (Floyd County Detention Center and Big Sandy Regional Detention Center).

To address barriers to service participation, grant funding will be used to provide evidence-based services to strengthen parenting skills for fathers who are incarcerated and planning for community re-entry, along with interventions to increase economic mobility and relationships. Individualized, culturally- /gender- competent and comprehensive case management and wraparound services will also foster program participation and success. The project will offer integrated services for fathers who are incarcerated in the targeted area who are incarcerated in Floyd County or Big Sandy facilities. Responsible parenting activities will include skills-based parenting education, dissemination of information regarding good parenting practices, one-on-one counseling regarding parenting issues, and will encourage and seek to facilitate the financial support of participants' children. Economic stability activities will include job readiness workshops, and upon release, linkages with additional job training and educational assistance, job search and placement assistance as well as employment incentives at 30 days of employment. Finally, healthy marriage/relationship activities will include marriage and relationship education, conflict resolution skills training, financial literacy seminars and counseling. Semi-annual parent/child events and annual relationship events will also be available to foster stronger family connections.

Objectives

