Following targeted screening, participants in the experimental (n=250) and comparison groups (n=250) will participate in baseline interviews focused on fatherhood, family relationships, and economic stability indicators, as well as factors which might impact these key outcomes including substance abuse and mental health. All participants in the local evaluation will also complete the post-test assessment at the conclusion of the courses (experimental group) or at a comparable time frame of 12 weeks for the comparison group. All evaluation participants will also be followed 6 months post-release from jail to complete an additional post-test assessment for the targeted instruments.

Study Population

The MCCC estimates that during the first year a minimum of 50 participants will be served accounting for up to a 9-month planning period. It is estimated that 150 participants will be served annually in years 2-5, with a final total of 650 participants over 5 years. Of these participating individuals, 250 will be randomly selected (50 each year of the 5 year project) to be involved in the local evaluation. In addition, 250 comparison group participants will be recruited from a non-treatment site (jail). The 500 total participants recruited for the local evaluation will be incarcerated fathers. Participants for the local evaluation will be identified as eligible fathers who have been tried and convicted as an adult; within 3 to 9 months of release; are low-income; and may be an expectant father, a biological father, an adoptive father or a stepfather or who a person who is acknowledged as a father figure (e.g., grandfather) of a dependent child or young adult child up to 24 years of age, and interested in participation. The target population does not exclude individuals from participants because of age, race, ethnicity, sexual orientation, culture, literacy, disability, or language.

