Data collection: Potential comparison group participants meeting study eligibility criteria will complete a face-to-face baseline interview with the study interviewer the same day of the initial screening session, which is expected to last about 1 hour. Treatment group participants will also complete the required assessment interviews with the research staff after being identified as being interested in the local evaluation. The interviewer will be trained in the study protocol, as well as in jail policies and procedures. Interviews will be conducted in the jail visiting rooms which are large enough to provide a confidential face-to-face interview, and have been used to conduct interviews for other studies with offenders. While jail staff may monitor participant entry and exit into the visitation room, no jail staff will be present for the confidential interviews.

Data collection for the evaluation will include the initial Fatherhood Pre-test for Incarcerated Fathers, followed by an interview with the Evaluation Coordinator (in person, phone, or Wi-Fi audio) at 12 weeks post-intake (or completion of services), and again at 6 months post-release from jail. Participants will receive incentives for their time to complete data collection interviews.

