Document Cover Page

Official Title of the Study:

Responsible Fatherhood Opportunities for Reentry & Mobility (ReFORM)

NCT Number: NCT02860988

Date of Document: January 15, 2020

STATISTICAL ANALYSIS PLAN

Analytic Sample:

The primary analysis sample will be used to address each primary research question. This sample consists of individuals with both baseline and six-month follow-up data.

Baseline equivalence between the intervention and comparison groups will be investigated for all demographic, criminal history, and other background characteristics. The equivalency of all primary and secondary outcome measures will also be investigated. Continuous variables will be compared using parametric (*t*-tests) and nonparametric (Wilcoxon rank-sum test) methods, whereas categorical variables will be compared using chi-square and Fisher's exact tests. All baseline equivalency measures will be performed with two-tail tests using an α of .05. Situations involving significant between group differences will be further characterized with effect sizes, using Hedges' *g* for the continuous outcomes and the Cox index for categorical outcomes. Any variables meeting the criteria of $p < .05$ will be discussed with the ETTA and considered for use as control variables for the analysis of primary and secondary outcomes. Other methods, for example, propensity score weights, will also be discussed if significant imbalance is observed.

Because the majority of services are provided in a jail setting, and the intervention and counterfactual samples are recruited from different institutions, the potential for condition crossover is not a concern.

Analytic Approach:

SPSS version 26 will be used to perform all analysis and data management. All parameters meeting the criteria $p < .05$, two-tailed, will be considered statistically significant. As the number of primary outcome measures is delimited, α corrections for multiple comparisons are not necessary. There will be no differences between how primary and secondary research questions are analyzed.

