The exact specification of the analytic model will depend on the nature of the outcome variable: continuous vs binary. In order to account for the longitudinal nature of the data, hierarchical linear models and hierarchical generalized linear models will be used to analyze continuous and binary outcomes, respectively. These methods allow for the nested structure of the data, where measurement occasion (level one) is nested within individual (level two), to be accounted for analytically.

Due to the quasi-experimental nature of the study design, simply controlling for baseline levels of the outcome of interest could be misleading since participants were not randomly assigned to the intervention vs counterfactual condition, and therefore have the potential to be significantly different at baseline. One method of accounting for these potential differences is to use a difference in differences model. Rather than controlling for baseline levels, the baseline value is instead considered as an additional timepoint and modeled as a difference score. The outcome is modeled as follows:

$$Y_i = \beta_0 + \beta_1 T_i + \beta_2 t_i + \beta_3 (T_i \times t_i) + \varepsilon_i$$

Where T is a dummy variable that takes on the value of 1 if individual i is in the intervention group and 0 otherwise, and t is a dummy variable that takes on the value of 1 for data from the six-month follow-up and 0 otherwise. The model terms can be interpreted as such:

β_0 – outcome mean for counterfactual condition at baseline

β_1 – difference in outcome mean between intervention and counterfactual at baseline

β_2 – change in outcome mean from baseline to six-month follow-up for counterfactual condition

β_3 – difference in the change in outcome means between intervention and counterfactual condition

As a result, the parameter of interest for determining an intervention difference is β_3 .

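### The only pre-period value is taken in jail, so for outcomes recorded as current community status, difference in differences removes little or none of any pre-existing gap between the groups

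*SAP*

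**What the plan says.** The SAP (Analytic Approach) notes that men were not randomly assigned and may differ at baseline, and offers difference in differences as one way to account for this: "Rather than controlling for baseline levels, the baseline value is instead considered as an additional timepoint and modeled as a difference score". The model has two time points, baseline (t=0) and six-month follow-up (t=1), and the effect is read from β_3. Continuous outcomes get hierarchical linear models and binary outcomes get hierarchical generalized linear models. The significance rule is p < .05, "two-tailed, will be considered statistically significant".

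The Protocol fixes where the baseline is taken. Under Study Population, "The 500 total participants recruited for the local evaluation will be incarcerated fathers", and eligibility requires release within 3 to 9 months. Under Research Procedures (Data collection), "Data collection for the evaluation will include the initial Fatherhood Pre-test for Incarcerated Fathers", and interviews take place in jail visiting rooms. The two later interviews are at 12 weeks post-intake (or completion of services) and at 6 months post-release, so the jail interview is the only measurement before the intervention.

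On content, the Study Design section says that "participants in the experimental (n=250) and comparison groups (n=250) will participate in baseline interviews focused on fatherhood, family relationships, and economic stability indicators", and the same sentence treats these domains as the key outcomes. Under Background, "Economic stability activities will include job readiness workshops, and upon release, linkages with additional job training and educational assistance". Neither document lists the individual outcome items, says whether they refer to the present or to the time before jail, or asks for a pre-incarceration value.

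**The concern.** Difference in differences removes a pre-existing gap only if the pre-period measurement shows that gap. A man in jail generally has no community job or wage and does not live with his child, whatever his history. If those outcomes are recorded as current status, both groups start from nearly the same low value and the baseline term has nothing to subtract.

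A real gap is plausible. Intervention men are approached at intake to a programme that includes job services. Comparison men are selected at random from another jail's daily census and then screened. The two groups share eligibility criteria but are not matched on work history or earlier involvement with their children. Any such difference that returns after release would be counted as programme effect.

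The SAP's own check would not show this on the affected outcome. Its equivalence test covers the outcome measures, but an outcome at a common floor looks balanced, so p < .05 will seldom be reached on it. Background characteristics are tested as well, but a significant result there leads only to control variables being considered and propensity weights being discussed.

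**Working it through.** **Inputs from the documents.** Two-sided α of 0.05 (SAP, Analytic Approach). 250 per group (Protocol, Study Design). Two time points, with β_3 as the effect (SAP, Analytic Approach). The documents state no power, event rate or effect size, so there is no figure of the plan's own to reproduce. The enrolment arithmetic is consistent: 50 × 5 = 250 and 250 + 250 = 500.

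**Assumed inputs.** Community employment of 50% in intervention men and 40% in comparison men, the same before jail and after release. No programme effect. An in-jail rate f that is equal in both groups.

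**Step 1: what β_3 estimates.** From the SAP model,

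β_3 = (Y1,post − Y0,post) − (Y1,pre − Y0,pre).

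If custody makes Y1,pre = Y0,pre, then β_3 = Y1,post − Y0,post, the raw follow-up difference. The same algebra holds for a continuous outcome such as earnings.

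**Step 2: linear scale, f = 0.** β_3 = (0.50 − 0.40) − 0 = +0.10, where the true effect is 0.

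- SE = √[(0.50×0.50 + 0.40×0.60)/250] = √(0.49/250) = 0.0443
- z = 0.10/0.0443 = 2.26, so the chance of p < .05 is about 62%

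For 45% v 40%, the chance is about 20%. With 175 per group (an assumed 30% loss) and comparison rates of 30% to 50%, a 10-point gap gives 47% to 50%. A 4,000-run simulation of 50% v 40% at 250 per group gave 0.61, 0.59 and 0.55 for floors of 0%, 2% and 5%. The linear result therefore does not need an exact floor.

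**Step 3: logit scale, small equal floors.** The SAP plans a generalized linear model for binary outcomes. It does not name the link, and logit is assumed here. The baseline log-odds cancel:

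β_3 = ln(0.50/0.50) − ln(0.40/0.60) = 0.405, OR 1.5.

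The bias is the whole pre-existing gap, but few baseline events make the estimate imprecise. A marginal Wald approximation, ignoring within-person correlation, gives

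Var(β_3) = 1/(250×0.25) + 1/(250×0.24) + 2/[250 f(1−f)].

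| Floor f | Variance | SE | z | Chance of p < .05 |
|---|---|---|---|---|
| 2% | 0.0160 + 0.0167 + 0.4082 = 0.441 | 0.664 | 0.61 | about 9% |
| 5% | 0.0160 + 0.0167 + 0.1684 = 0.201 | 0.448 | 0.90 | about 15% |

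For 45% v 40%, the same formula gives about 6% and 7%.

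**Step 4: logit scale, f = 0 exactly.** The baseline log-odds are unbounded, so neither β_1 nor β_3 has a finite estimate.

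**Step 5: pre-incarceration value as t=0.** If that value shows the same 10-point gap, β_3 = 0.10 − 0.10 = 0. Simulation on the linear scale gave rejection of 0.053 at 250 per group and 0.051 at 175. This rests on the assumption that the gap is stable from before jail to after release.

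**The case against.** The strongest reply is that the premise depends on an instrument the reader cannot see. The documents name domains, not items, and the baseline form is titled for incarcerated fathers. If its economic or father-child items ask about the period before jail, the floor does not arise for them and the remedy is already in place. This stands, and it makes the point conditional.

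A reader might infer that difference in differences cannot work for any fatherhood or economic outcome. The documents do not support that. Contact by visits or calls can vary in custody, so part of a pre-existing gap may be removed. Attitude and skill scales need not be at a floor.

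A reader might also take 62% as the false-positive rate of the planned binary analysis. It is not. It belongs to a linear difference in proportions. Under a logit model the bias remains, but the rejection rate is far lower, as the working shows.

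Other protections exist. The SAP also tests demographic, criminal-history and other background characteristics, the eligibility criteria (including low income and time to release) are common to both groups, and the Protocol describes the jails as comparable. These reduce the risk. But the comparability is asserted without data, and the SAP does not commit to any adjustment.

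Finally, a pre-incarceration baseline gives β_3 = 0 in the illustration only because a stable gap is assumed. That is correct, and it is a limit of the remedy.

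**Conclusion.** The point holds conditionally and is worth acting on. For any outcome that is recorded as current status and held near a common floor by custody, the in-jail baseline carries little or no information on community differences. β_3 is then close to an unadjusted six-month comparison between non-randomised jails, and the equivalence check on that outcome offers no warning.

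Under the assumed 50% v 40%, the bias is the full gap: +10 points on the linear scale, or 0.405 in log odds. The effect on error rates depends on the model. Against a nominal 5%, rejection is about 62% in a linear analysis and about 9% to 15% in a logit model with floors of 2% to 5%. With no baseline events at all, the logit model fails to give a finite β_3. All rates are assumptions, since the documents supply none. Whether any outcome is affected depends on items and recall windows that the documents do not state, and that omission alone justifies a clarification.

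**What to change.** 1. In the SAP (Analytic Approach), state the reference period of every outcome at t=0 and t=1.
2. For community-status outcomes, define t=0 as the value for a fixed period before the current incarceration. Collect it in the baseline interview of both groups, or take it from the pre-test where its items already refer to that period.
3. Keep the in-jail value as t=0 for attitude and skill scales.
4. Include the pre-incarceration values in the SAP's baseline equivalence check (Analytic Sample), and commit in advance to adjusting for pre-incarceration work and father-child history, whatever the p-value.
5. For men already enrolled without these items, use retrospective answers from a later interview only in a labelled sensitivity analysis, because intervention men would give them after exposure to services.

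The cost is a few questions in an interview of about an hour and a short SAP addition. There are two drawbacks: recall error may differ between the groups, and the analysis would still assume parallel trends from before jail to after release. The SAP should state that assumption.

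### Does the SAP's silence on the 12-week assessment, with time coded zero for everything but six months, put the treatment comparison at risk?

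*SAP*

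**What the plan says.** The protocol (Study Design) schedules a middle assessment for both groups: "All participants in the local evaluation will also complete the post-test assessment at the conclusion of the courses (experimental group"), or after 12 weeks in the comparison group. A further assessment follows six months after release. The Data collection paragraph under Research Procedures repeats this schedule, timing the middle interview at 12 weeks from intake or at completion of services.

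The SAP names only two of these occasions. Under Analytic Sample, the primary sample is defined by person: "This sample consists of individuals with both baseline and six-month follow-up data". Under Analytic Approach, "hierarchical linear models and hierarchical generalized linear models will be used to analyze continuous and binary outcomes, respectively", with a data structure "where measurement occasion (level one) is nested within individual (level two"). Time enters through one indicator: "t is a dummy variable that takes on the value of 1 for data from the six-month follow-up and 0 otherwise".

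The coefficients are then defined in words. β_0 is the comparison-group mean at baseline, β_1 the group difference at baseline, β_2 the "change in outcome mean from baseline to six-month follow-up for counterfactual condition", and β_3 the difference between groups in that change. β_3 is the parameter of interest. On secondary questions the SAP adds: "There will be no differences between how primary and secondary research questions are analyzed". It does not list the primary or secondary research questions.

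**The concern.** Two things look wrong.

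**Coding.** The model is written for measurement occasions, and a 12-week interview is a measurement occasion that is not the six-month one. Taken word for word, the coding rule gives it t = 0 and so merges it with baseline. The sample rule does not prevent this, since it selects men and not records. If the courses had worked by week 12, part of the benefit would sit in the reference level and be subtracted from the six-month effect.

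**Omission.** A two-group outcome assessment is collected and given no stated analysis. Men enrol 3 to 9 months before release, so the six-month interview falls about 9 to 15 months after enrolment. The middle assessment is the one closest to the courses, and the SAP itself notes that "the majority of services are provided in a jail setting". With nothing stated, that contrast would be either unused or specified after the data are seen.

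**Working it through.** The documents give no power, effect size, SD or dropout rate, so there is no planned figure to reproduce. Effects below are in SD units. Δ12 and Δ6 are the true differences between groups in change from baseline at the middle and six-month assessments. Their values are assumptions.

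**1. What the literal coding would estimate.** With three complete records coded 0, 0, 1, the within-man time slope is Y6 − (Y0 + Y12)/2. The baseline group difference cancels, so

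β_3 = Δ6 − ½Δ12.

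With baseline and six-month records only, β_3 = Δ6. A simulation (250 per group, within-man correlation about 0.5, 200 replicates) agrees:

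| Δ12 | Δ6 | Two occasions, simulated | 12-week rows at t = 0, formula | 12-week rows at t = 0, simulated |
|---|---|---|---|---|
| 0 | 0.30 | 0.304 | 0.30 | 0.303 |
| 0.15 | 0.30 | 0.300 | 0.225 | 0.222 |
| 0.30 | 0.30 | 0.310 | 0.15 | 0.153 |
| 0.60 | 0.30 | 0.289 | 0 | −0.013 |
| 0.30 | 0 | 0.007 | −0.15 | −0.139 |

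The distortion would be serious if anyone analysed the data that way.

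**2. Whether the SAP permits that reading.** Let c12 and c6 be the comparison group's mean changes from baseline. Under the literal coding with complete records:

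- β_0 = baseline mean + ½c12. The SAP says baseline mean.
- β_1 = baseline difference + ½Δ12. The SAP says baseline difference.
- β_2 = c6 − ½c12. The SAP says the change from baseline to six months, which is c6.
- β_3 = Δ6 − ½Δ12. The SAP says the group difference in that change, which is Δ6.

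All four conflict with the SAP's definitions unless c12 = 0 and Δ12 = 0. With t = 0 meaning baseline alone, all four match. The paragraph before the equation points the same way: it treats baseline as a time point and works with the difference from it. The sample rule also asks for exactly those two occasions.

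**3. What a course-end contrast could offer.** Under compound symmetry with SD 1, n per group and within-man correlation ρ, SE = √(4(1 − ρ)/n). At ρ = 0.5 this is 0.0894, 0.1000 and 0.1155 for n = 250, 200 and 150 (100%, 80% and 60% of the planned 250). The effect detectable with 80% power at two-sided 0.05 is 2.80 × SE = 0.25, 0.28 and 0.32 SD. At n = 250 it is 0.30 for ρ = 0.3 and 0.19 for ρ = 0.7. Such an analysis would be feasible, but these figures do not measure a fault in the plan.

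**4. Its limits.** Twelve weeks is 2.76 months. A man interviewed at exactly 12 weeks has 3 − 2.76 = 0.24 to 9 − 2.76 = 6.24 months left before release. He is generally still in jail, so employment and most outcomes of life after release cannot yet be observed. Some services begin only on release (protocol, Background), so the contrast is not an end-of-programme effect. For treated men the interview follows the end of the courses, whose length is not given, so its timing can differ between groups.

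**5. Its cost in error rate.** The two estimates share baseline: covariance 1 − ρ, variance 2(1 − ρ), correlation 0.5 if the same men are used. For one outcome, the chance of at least one false positive in two null tests rises from 5% to about 9% (0.091). The SAP applies no multiplicity correction, and several outcomes would raise the figure further.

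**The case for a change.** The best case for a change is this. In the documents, the comparison men's 12-week interview belongs only to the two-group evaluation, because the separate performance-measure component covers programme clients. The stated aim is the effectiveness of the services, most of which are delivered in jail. The SAP says it covers secondary questions as well, yet gives this interview no role. Stating one would need no new data, and text that can be coded wrongly sometimes is.

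Part of this stands. The role of the 12-week records is not stated, and no sentence expressly restricts the model to two occasions. A 12-week group contrast reported later could not be presented as specified in this SAP.

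The rest does not carry. The coding risk requires an analyst to ignore four coefficient definitions and the account of the method beside the equation. The loss of a course-end estimate cannot be established, because the research questions are not listed. If a secondary question does concern course end, the instruction to analyse secondary questions alike points to the same model form with that assessment in place of six months. The restriction to men with six-month data is stated for the primary questions. A six-month endpoint is also a reasonable choice for a re-entry programme aimed at employment, relationships and contact with children after release.

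**Conclusion.** No change to the plan follows. The coding phrase is loose wording whose meaning the SAP's coefficient definitions settle: t = 0 is baseline. Read so, β_3 is the baseline-to-six-month difference in differences, and this point affects neither its estimate nor its error rate. The shift of half the 12-week effect (0.15 SD when that effect is assumed to be 0.30) belongs to a misreading and not to the planned analysis.

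The silence on the middle assessment is missing detail, and concentrating on six months is a fair trade-off. A separate course-end model would be defensible but optional. It could detect about 0.25 to 0.32 SD under the assumptions above (ρ = 0.5, 60% to 100% follow-up), only for outcomes measurable in jail and with timing that differs by group. It would raise the false-positive chance per outcome from 5% to about 9%.

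This conclusion rests on the analyst following the SAP's own definitions of β_0 to β_3. It concerns only the handling of the 12-week records, not other sources of bias in a comparison between jails.

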The ACF award to MCCC primarily supports service enhancement and service delivery. To ensure the effectiveness of the proposed services, MCCC will be contracting with University of Kentucky to perform the evaluation. The evaluation includes two primary components:

- 1) consultation on the collection of ACF required Performance Measures to document program client characteristics, program operations, enrollment and participation, and pre-test/post-test outcome measures; and
- 2) responsibility for the local evaluation which includes a quasi-experimental two group design to examine the effectiveness of targeted services for fathers at MCCC

Study Design

The local evaluation will utilize a quasi-experimental research design including an experimental group (receives MCCC targeted services under the newly funded ACF grant) and a comparison group (incarcerated fathers who do not receive targeted services in a comparable local regional jail). The Kentucky River Regional Jail (KRRJ) is selected as the site for comparison group recruitment because it does not fall in the Mountain Comprehensive Care designated service region, and individuals residing in the KRRJ are comparable in demographics and other key variables of interest.

In the proposed evaluation, eligibility criteria used to select participants for the targeted MCCC grant-funded services in the Floyd County Detention Center and the Big Sandy Regional Detention Center will also be implemented in a comparison jail site. The Kentucky River Regional Jail (KRRJ) located in Hazard, Kentucky is not in the targeted service area for this MCCC project. KRRJ is comparable in size, characteristics of the offender population, and geographic location to the targeted facilities in Floyd County and Big Sandy. Following standardized screening based on grant eligibility criteria, the only anticipated difference between the experimental condition and the comparison condition is the opportunity to receive targeted services based on jail.

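### Must the SAP spell out the parallel-change assumption before β_3 can serve as the intervention difference, when jail alone decides condition?

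*SAP*

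**What the plan says.** Under Analytic Approach, the SAP regresses the outcome on group, time and their product. It defines β_3 as "difference in the change in outcome means between intervention and counterfactual condition" and concludes: "As a result, the parameter of interest for determining an intervention difference is" β_3. Significance is two-tailed at .05. The stated reason for the model is that "participants were not randomly assigned to the intervention vs counterfactual condition, and therefore have the potential to be significantly different at baseline".

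Under Analytic Sample, the SAP limits the primary sample: "This sample consists of individuals with both baseline and six-month follow-up data". Background variables that differ between groups at p < .05 are to be "considered for use as control variables for the analysis of primary and secondary outcomes", with propensity weights as a further option. Separate jails are mentioned only for contamination: "the intervention and counterfactual samples are recruited from different institutions, the potential for condition crossover is not a concern".

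The Protocol (Study Design; Subject Recruitment Methods and Privacy) takes 250 intervention men from Floyd County and Big Sandy and 250 comparison men from Kentucky River. It justifies Kentucky River by its similar size, inmate population and location, and adds that "the only anticipated difference between the experimental condition and the comparison condition is the opportunity to receive targeted services based on jail". Men have "baseline interviews focused on fatherhood, family relationships, and economic stability indicators", then assessments at about 12 weeks and at 6 months after release.

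**The concern.** Difference in differences removes group differences that stay constant over time. It does not remove differences in how the groups would have changed anyway. Here jail and condition coincide completely, so any such difference goes straight into β_3. The SAP discusses non-randomisation only as a matter of starting levels, explains each coefficient, and then moves from a neutral difference in change to an intervention difference without naming the condition that permits the step.

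The setting makes this more than a formality. Men enter 3 to 9 months before release and the key assessment is 6 months after it. The change therefore includes the return to the community, and the outcomes include economic stability, which local conditions could affect. If the groups drifted apart for reasons unrelated to the programme, a significant β_3 could be reported as evidence that the programme works.

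**Working it through.** **1. What β_3 estimates.** Let d be the difference between the groups in the change they would have shown without the programme. Then the expected value of β_3 is the programme effect plus d. Stable differences go into β_1. With one assessment before services, d cannot be estimated from the planned data.

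**2. Length of the change.** From the Protocol's entry window and follow-up: 3 + 6 = 9 months to 9 + 6 = 15 months.

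**3. How close the Protocol comes.** If access to services really is the only difference between conditions, equal change without services follows. The sentence is an assertion about comparability and is not phrased as a condition on change, but its content covers most of what seems to be missing.

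**4. Possible size (illustrative).** The documents give no effect size, SD, correlation or retention rate, so there is no planned figure to reproduce. Inputs: 250 per arm from the Protocol; 200 and 125 analysed per arm assumed; d assumed; continuous outcomes; change-score SD units.

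- SE = sqrt(2/N): 0.0894 at 250, 0.1000 at 200, 0.1265 at 125.
- With no programme effect, P(p < .05) = 1 − Φ(1.96 − d/SE) + Φ(−1.96 − d/SE).
- Example, N = 250 and d = 0.10: d/SE = 1.118, so P = 1 − Φ(0.842) + Φ(−3.078) = 0.200 + 0.001 = 0.201.

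| d (SD) | 250 per arm | 200 per arm | 125 per arm |
|---|---|---|---|
| 0 | 5% | 5% | 5% |
| 0.05 | 8.6% | 7.9% | 6.8% |
| 0.10 | 20% | 17% | 12% |
| 0.15 | 39% | 32% | 22% |

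In SDs of the outcome itself, SE = sqrt(2(1 − ρ)) × sqrt(2/N). For an assumed baseline-to-follow-up correlation ρ of 0.3 to 0.7 and N = 250, this is 0.1058 to 0.0693, and d = 0.10 gives 16% to 30%.

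**5. What each possible change would achieve.**

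- *A sentence stating the assumption.* Model, sample, estimate, interval and p-value all stay as they are.
- *Separate contrasts for Floyd County and Big Sandy against Kentucky River.* With an assumed 125/125/250 split, SE = sqrt(1/125 + 1/250) = 0.110 SD, against 0.089 pooled. Floyd County minus Big Sandy has SE = sqrt(1/125 + 1/125) = 0.126 SD and carries no information about Kentucky River. None of these tests equal change.
- *A table of β_3 over assumed values of d.* This only shifts the reported interval. For an observed β_3 of 0.25 SD at 250 per arm, the lower limit is 0.25 − 1.96 × 0.0894 = 0.075, so d = 0.075 SD brings it to zero. Any reader can do this from the published interval.
- *Baseline covariates.* With complete pairs, subtracting the two occasions gives Y(follow-up) − Y(baseline) = β_2 + β_3T + error. A baseline covariate entered as a main effect cancels, so β_3 in the linear model does not move. Only an interaction with time, or weighting, could act on measured sources of d.

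**The case for a change.** The strongest case for a change is that the evaluation sets out to examine effectiveness, so β_3 will be read causally. Since the data cannot check the assumption, open statement is the only safeguard, and it costs a sentence. The Protocol's comparability claim is asserted, is not carried into the SAP, and is not about change over time. The threat is also wider than jail or area. Intervention men are service recipients who sign a release, while comparison men are first drawn at random from the daily census and then screened. The two groups could follow different courses even if local conditions moved identically.

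Much of this stands. The assumption is unstated and untestable here, and the different routes into the study are a reason to doubt it. The SAP's covariate provision does not answer the point unless covariates are interacted with time or used in weights. What does not stand is that the plan misleads. It says openly that assignment was not random, chooses difference in differences for that reason, and defines β_3 descriptively. Its final sentence speaks of an intervention difference, and the .05 rule only labels results statistically significant. Neither prescribes a causal claim.

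**Conclusion.** No change to the plan is needed. The SAP leaves unstated the textbook condition of a method it names, in a design both documents describe as quasi-experimental. An analyst who uses difference in differences will know that it rests on equal change in the two groups of men and can be expected to say so when reporting. Stating it in advance would change no result, and the additional analyses considered here would not test it.

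The underlying uncertainty is not trivial: under the assumed differences of 0.05 to 0.15 change-score SD, false-positive rates run from 6.8% to 39% across 125 to 250 analysed per arm. That uncertainty belongs to the choice of three jails and one assessment before services, and SAP wording cannot reduce it. The figures rest on assumed values of d and of the numbers analysed, apply to continuous outcomes, and give no direction for any bias; none is offered for binary outcomes. The conclusion would differ if the documents committed the evaluators to an unqualified causal claim from p < .05 on β_3, which they do not.
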